**Of note: Rifampicin or Rifapentine are not allowed for TB prophylaxis.**

Subjects with a prior history of latent TB that have documented completion of a full course of anti-TB therapy per local guidelines within 1 year prior to first study drug administration will be allowed to enter the study provided nothing has changed in the subject's medical history to warrant repeat treatment.

Subjects with documented completion of a full course of anti-TB therapy greater than 1 year prior to first study drug administration may be allowed to enter the study only after consultation with the AbbVie Therapeutic Area Medical Director.

Newly initiated prophylactic treatment should be captured in the eCRF and in the source documents. Prior therapy should be captured in the eCRF.

*Period 2*

Subjects with documentation of prior positive result of QuantiFERON-TB Gold Test (or equivalent) and/or PPD are not required to repeat either TB test during the study and should be considered positive. The TB risk assessment form will be completed annually for all subjects, regardless of TB test results.

For subjects with a negative QuantiFERON®-TB Gold (and/or PPD) test at Screening, a QuantiFERON®-TB Gold (and/or PPD) re-test will be performed (or both if required by local guidelines) at Week 48 as indicated in [Table 5](#). Subjects from China will have additional re-tests at Week 12 and Week 24. If the QuantiFERON®-TB Gold test is indeterminate, then the investigator should perform a local QuantiFERON®-TB Gold test (or through the central laboratory if not locally available) to rule out a positive test result. If testing remains indeterminate or is positive, then the subject is considered to be positive for the purpose of this study. If the local testing result is negative, then the patient is considered to be negative. If one of these subsequent tests has a positive test result (seroconversion), a chest x-ray (CXR) needs to be performed as soon as possible to aid in distinguishing active versus latent TB. Expert consultation can be considered per

Investigator's discretion. Any positive TB screen after the patient has started the study, should be reported as an adverse event (AE) of latent or active TB (as applicable).

Obtain a CXR for subjects with TB risk factors as identified by the TB risk assessment form (Appendix E) or for subjects living in areas endemic for TB or for subjects with newly positive PPD or QuantiFERON®-TB Gold test.

Subjects with new evidence of latent TB should initiate prophylactic treatment immediately per local guidelines and complete at least 6 months of prophylaxis. TB prophylaxis should be initiated and study drug(s) should not be withheld. Two to 4 weeks later (per local guidelines), the subject should be re-evaluated (unscheduled visit) for signs and symptoms as well as laboratory assessment of toxicity to TB prophylaxis.

Newly initiated prophylactic treatment and prior therapy should be captured in the eCRF.

If the subject is experiencing signs or symptoms suspicious for TB or something has changed in the subject's medical history to warrant a repeat test before the next scheduled annual TB re-test, a repeat test should be performed as soon as possible and the case (including the TB test results) must be discussed with the AbbVie Therapeutic Area Medical Director.

### **Chest X-Ray (CXR)**

A CXR (posterior-anterior and lateral views) is required:

- For all subjects at Screening to rule out the presence of TB or other clinically relevant findings. The CXR will not be required if the subject had a previous normal CXR (posterior-anterior and lateral views) within 90 days of Screening, provided all source documentation is available at the site as outlined below and provided nothing has changed in the subject's medical history to warrant a repeat test.
- For all subjects at Week 48. Subjects from China will have an additional CXR performed at Week 24.

Subjects can have a repeat CXR at any time during the study as warranted, based on the opinion of the Investigator.

A radiologist or pulmonologist must perform an assessment of the CXR. The Principal Investigator will indicate the clinical significance of any findings and will sign and date the report. In the assessment of the CXR, the Principal Investigator or their delegate must indicate the presence or absence of (1) calcified granulomas, (2) pleural scarring/thickening, and (3) signs of active TB. If the CXR demonstrates changes suggestive of previous TB (e.g., calcified nodule, fibrotic scar, apical or basilar pleural thickening) or other findings that are clinically significant, the Principal Investigator should contact the AbbVie Therapeutic Area Medical Director before enrolling the subject.

### **12-Lead ECG**

A resting 12-lead ECG will be performed at the designated study visits as specified in [Table 3](#) and [Table 5](#). A qualified physician will interpret the clinical significance of any abnormal finding, sign, and date each ECG. ECG with QT interval corrected for heart rate using Friedericia's correction formula (QTcF) should be reported (or calculated) and documented in the source documents and later transcribed on to the appropriate eCRF if QTcF prolongation is observed. A valid QTcF cannot be calculated in subjects who have a pacemaker or supraventricular or ventricular conduction abnormalities. In these cases, the baseline QTcF will need to be entered into the appropriate eCRF for comparison as well. In addition, any clinically significant findings will be documented in the source documents and later transcribed on to the appropriate eCRF. Each signed original ECG will be monitored by the responsible site monitor and kept with subject's source documents onsite.

For subjects with a normal ECG taken within 90 days of Screening, a repeat ECG at Screening will not be required, provided source documentation is available and provided nothing has changed in the subject's medical history to warrant a repeat test. If there are

---

other findings that are clinically significant, the Investigator must contact the AbbVie Therapeutic Area Medical Director before enrolling the subject.

Subjects can have a repeat ECG at any time during the study as warranted based on the opinion of the Investigator.

### **Height and Weight**

Height will be measured at the Screening Visit only (with shoes off). Body weight will be measured at all scheduled visits except Week 1 as specified in [Table 3](#) and [Table 5](#). All measurements will be recorded in metric units where applicable.

### **Vital Signs**

Vital sign determinations of systolic and diastolic blood pressure in sitting position, pulse rate, respiratory rate, and body temperature will be obtained at visits specified in [Table 3](#) and [Table 5](#). Blood pressure, pulse rate, body temperature, and respiratory rate should be performed before blood draws are performed.

### **Physical Examination**

A complete physical examination will be performed at the designated study visits as specified in [Table 3](#) and [Table 5](#). The physical examination at the Baseline Visit will serve as the baseline physical examination for the entire study. Physical examination abnormalities noted by the Investigator at Baseline prior to the first dose of study drug will be recorded in the subject's medical history; abnormalities noted after the first dose of study drug will be evaluated and documented by the Investigator as to whether or not the abnormality is an AE (see Section [6.1.1.1](#) for AE definition). All findings, whether related to an AE or part of each subject's medical history, will be captured on the appropriate eCRF page.

At any time, a symptom-directed physical examination can be performed as deemed necessary by the Investigator.

**Physician Global Assessment of Disease Activity VAS**

At visits specified in [Table 3](#) and [Table 5](#), the Physician will rate global assessment of subject's current disease activity ranging from 0 to 100 independent of the subject's self-assessment using the VAS, which consists of a horizontal 100 mm line anchored at either end by opposite adjectives reflecting the spectrum/severity of the parameters assessed ([Appendix C](#)).

**TJC and SJC Assessment***TJC Assessment*

An assessment of 68 joints ([Appendix D](#)) will be done for tenderness by pressure manipulation on physical examination at visits specified in [Table 3](#) and [Table 5](#). Joint pain/tenderness will be classified as: present ("1"), absent ("0"), replaced ("9") or no assessment ("NA").

*SJC Assessment*

An assessment of 66 joints ([Appendix D](#)) will be done by directed physical examination at visits specified in [Table 3](#) and [Table 5](#). The joints to be examined for swelling are the same as those examined for tenderness, except the hip joints are excluded. Joint swelling will be classified as present ("1"), absent ("0"), replaced ("9") or no assessment ("NA").

Any injected joints will be considered as "not assessed" ("NA") for 3 months from the time of the intra-articular injection.

If possible, the TJC and SJC should be performed by an independent and blinded joint assessor who should not perform any other study related procedures.

In order to minimize variability, the same independent joint assessor should evaluate the subject at each visit for the duration of the trial as much as possible. A back-up independent joint assessor should be identified. The independent joint assessor should be a qualified medical professional (e.g., nurse, physician's assistant, physician). Any other

joint assessor must be trained and competent in performing such assessments. It is the responsibility of the Investigator to ensure that all assessors are qualified and trained to perform joint assessments. If the independent assessor is not available, the pre-identified back-up assessor should perform such assessments.

### **CDAI**

The CDAI calculation is required to determine if a subject fails to achieve low disease activity at the Week 24 visit. An Interactive Response Technology (IRT) will calculate CDAI with input from site personnel on joint counts and the subject's and physician's Global Assessment of RA Disease Activity score. A worksheet will be provided to capture the components required for IRT entry to obtain the CDAI calculation.

The calculation used to determine CDAI score at Week 24 is as follows:

$$\text{CDAI} = \text{TJC28} + \text{SJC28} + \text{PtGA (cm)} + \text{PhGA (cm)}$$

NOTE: Investigator should optimize background RA therapies in subjects who failed to achieve a CDAI  $\leq 10$ .

### **Pregnancy Testing**

A serum pregnancy test will be performed for all women of childbearing potential at the Screening Visit. The serum pregnancy test will be sent to and performed by the central laboratory. If the serum pregnancy test is positive the subject is considered a screen failure. If the serum pregnancy test is borderline, it should be repeated  $\geq 3$  days later to determine eligibility. If the repeat serum pregnancy test is:

- Positive, the subject is considered a screen failure;
- Negative, the subject can be enrolled into the trial;
- Still borderline  $\geq 3$  days later, this will be considered documentation of continued lack of a positive result and the subject can be enrolled into the study.

In Period 1, a urine pregnancy test will be performed for all women of childbearing potential at the Baseline Visit prior to the first dose of study drug and all subsequent visits except Week 1. More frequent pregnancy tests will be performed throughout the study if required per local/country requirements.

- If the baseline urine pregnancy test performed at the site is negative, then dosing with study drug may begin.
- If the baseline or post-baseline urine pregnancy test performed at the site is positive, dosing with study drug must be withheld and a serum pregnancy test is required. The serum pregnancy test will be sent to and performed by the central laboratory. If the serum pregnancy test is negative, study drug may be started or resumed. If the serum pregnancy test is positive, study drug must be permanently discontinued and the subject must be discontinued from the study. In the event a serum pregnancy test comes back borderline, a repeat test is required ( $\geq 3$  days later) to document continued lack of a positive result.

In Period 2, for women of childbearing potential, a urine pregnancy test will be performed at all visits, including the 30 days follow-up visit, and starting at Week 24 a urine pregnancy test will be performed monthly at home between scheduled study visits. The results of the monthly at home tests will be communicated to the site. If a urine pregnancy test is positive, the subject must stop dosing, come in to the clinic and have blood drawn for a serum pregnancy test that will be analyzed at the central laboratory.

At each visit, the study staff should review the pregnancy avoidance recommendations with women of childbearing potential and male subjects with a partner of childbearing potential, and document this discussion in the subject's source records.

If during the course of the study a woman becomes surgically sterile or post-menopausal and complete documentation as described in Section 5.2.4 is available, pregnancy testing is no longer required.

A pregnant or breastfeeding female will not be eligible for participation or continuation in this study.

### **Clinical Laboratory Tests**

Samples will be obtained for the clinical laboratory tests listed in [Table 6](#). Unscheduled clinical labs may be obtained at any time during the study if deemed appropriate per Investigator's discretion. A certified central laboratory will be utilized to process and provide results for the clinical laboratory tests. All abnormal laboratory tests that are considered clinically significant by the Investigator will be followed to a satisfactory resolution.

The central laboratory chosen for this study will provide instructions regarding the collection, processing, and shipping of these samples.

Blood samples will be obtained for the laboratory tests at visits specified in [Table 3](#) and [Table 5](#). Blood draws should be performed only after all clinical assessments and questionnaires (HAQ-DI, Patient's Assessment of Pain, etc.) and vital sign determinations are obtained.

For clinic visits where samples for serum chemistry tests are collected, subjects should be fasting (a minimum 8-hour fast) whenever possible. If a subject is not able to fast when necessary, due to unforeseen circumstances, the non-fasting status will be recorded in study source documentation.

Urine samples will be obtained for urinalysis testing at visits specified in [Table 3](#) and [Table 5](#). The central laboratory will be responsible for performing a macroscopic urinalysis (urine dipstick) on the collected urine specimens. Specified abnormal macroscopic urinalyses defined as leukocytes, nitrite, protein, ketones, or blood greater than negative, or glucose greater than normal will be followed up with a microscopic analysis at the central laboratory.

For any laboratory test value outside the reference range that the Investigator considers to be clinically significant, the Investigator should apply the standard of care for medical evaluation and treatment per local guidelines:

- The Investigator will repeat the test to verify the out-of-range value.
- The Investigator will follow the out-of-range value to a satisfactory clinical resolution.

A laboratory test value that requires a subject to be discontinued from the study drug or requires a subject to receive treatment will be recorded as an AE.

**Table 6. Clinical Laboratory Tests**

Hematology (Central Lab)	Clinical Chemistry a (Central Lab)	Urinalysis b (Central Lab)	Other Laboratory Tests
Hematocrit	BUN	Specific gravity	Central Lab Tests:
Hemoglobin	Creatinine	Ketones	Serum pregnancy (bHCG) test d
RBC count	Total bilirubin	pH	HBs Ag e
WBC count	INR (reflex only) c	Protein	HBs Ab e
Neutrophils	ALT	Blood	HBc Ab e
Bands	AST	Glucose	HBV DNA PCR reflex only e
Lymphocytes	Alkaline phosphatase	Urobilinogen	HCV Ab e
Monocytes	CPK	Bilirubin	HCV RNA (reflex only) e
Basophils	Sodium	Leukocytes	QuantiFERON-TB Gold f
Eosinophils	Potassium	Nitrites	HIV-1 e,g
Platelet count	Chloride	Microscopic examination, if needed	HIV-2 e,g
	Bicarbonate		HAV-IgM e
	Calcium		Syphilis antibody (in mainland China only) e
	Inorganic phosphate		Rheumatoid Factor e
	Uric acid		Anti-CCP autoantibodies e
	Cholesterol		hs-CRP h
	LDL-C		IgG and IgM
	HDL-C		FSH i
	Total protein		Local Lab Tests:
	Glucose		Urine pregnancy test j
	Triglycerides		ESR
	Albumin		MRB Panel k

ALT = alanine aminotransferase; AST = aspartate aminotransferase; bHCG = beta human chorionic gonadotropin; BUN = blood urea nitrogen; CCP = cyclic citrullinated peptide; CPK = creatine phosphokinase; DNA = deoxyribonucleic acid; ESR = erythrocyte sedimentation rate; HBc Ab = hepatitis B core antibody; HBs Ab = hepatitis B surface antibody; HBs Ag = hepatitis B surface antigen; HBV = hepatitis B virus; HCV Ab = hepatitis C virus antibody; HDL-C = high-density lipoprotein cholesterol; HIV = human immunodeficiency virus; hsCRP = high-sensitivity C-reactive protein; IgG = immunoglobulin G; IgM = immunoglobulin M; IN = international normalized ratio; LDL C = low density lipoprotein cholesterol; PCR = polymerase chain reaction; RBC = red blood cell; RNA = ribonucleic acid; TB = tuberculosis; WBC = white blood cell

**Table 6. Clinical Laboratory Tests (Continued)**

- a. Minimum 8-hour fast. If a subject is not able to fast when necessary, due to unforeseen circumstances, the non-fasting status will be recorded in study source documentation.
- b. A urine dipstick macroscopic urinalysis will be completed by the central laboratory at all required visits. A microscopic analysis will be performed in the event the dipstick results show leukocytes, nitrite, protein, ketones, or blood greater than negative or glucose greater than normal.
- c. INR will only be measured with a separate blood sample at repeat testing if ALT and/or AST  $> 3 \times$  ULN.
- d. A serum pregnancy test will be performed for all women of childbearing potential at the Screening Visit and if postbaseline urine pregnancy test turns positive.
- e. At Screening only. For mainland China only, subjects with HBs Ab+ and/or HBc Ab+ and negative HBV DNA at screening, HBV DNA PCR test should be performed every 12 weeks. HBV DNA PCR testing every 12 weeks is not necessary when the subject has a history of HBV vaccine and HBs Ab+.  
HBV DNA testing is also required for subjects who meet specific toxicity management criteria (See ALT/AST toxicity management criteria in Table 8).
- f. If PPD not performed.
- g. Subjects will be tested for antibodies to HIV at Screening. The results of the HIV Ab testing will be retained by the study site under confidential restriction. A subject will not be eligible for study participation if test results indicate a positive HIV infection. AbbVie will not receive results from the testing and will not be made aware of any positive result.
- h. The hsCRP results starting from baseline (Day 1) will not be reported to the Sponsor, Investigator, study site personnel, and the subject. hsCRP will be performed by the Central Lab. Local laboratory or site testing for hsCRP or CRP is not allowed after Baseline. Results of tests such as hsCRP may be blunted in subjects taking a JAK inhibitor, thereby limiting the clinical utility of these tests in the setting of a possible safety assessment or adverse event management. Any local hsCRP or local CRP tests should not be reported to the investigator until a subject completes Period 1. During open label study conduct hs-CRP may be reported to the Sponsor, Investigator, study site personnel, and/or the subject.
- i. For more details, please refer to Section 5.2.4 (Contraception Recommendations).
- j. A urine pregnancy test will be performed for all women of childbearing potential at the Baseline Visit prior to the first dose of study drug and all subsequent visits except Week 1. If the baseline urine pregnancy test performed at the site is negative, then dosing with study drug may begin. If the baseline urine pregnancy test performed at the site is positive, dosing with study drug must be withheld and a serum pregnancy test is required. The serum pregnancy test will be sent to and performed by the central laboratory. If the serum pregnancy test is positive, study drug must be withheld and the subject must be discontinued from the study. In the event a pregnancy test comes back borderline, a repeat test is required ( $\geq 3$  days later) to document continued lack of a positive result. If a urine pregnancy test postbaseline is positive, study drug needs to be temporarily discontinued and a serum pregnancy test is required. The serum pregnancy test will be sent to and performed by the central laboratory. If serum pregnancy test is negative, study drug may be restarted. If the serum pregnancy test is positive, study drug must be permanently discontinued.
- k. If needed to assess B cell counts in subjects who have discontinued rituximab, see Inclusion Criteria 7.

## **Hepatitis Screen**

All subjects will be tested for the presence of HAV, HBV and HCV at Screening.

### *Hepatitis A:*

Blood samples for hepatitis A serology will be obtained at the Screening Visit. A subject will not be eligible for study participation in case of positive test result for hepatitis A virus immunoglobulin M (HAV-IgM).

### *Hepatitis B:*

Subjects will be tested for the presence of HBV at screening using the following tests:

- HBs Ag (Hepatitis B surface antigen)
- HBc Ab/anti-HBc (Hepatitis B core antibody)
- HBs Ab/anti-HBs (hepatitis B surface antibody)

[figure not shown]
A positive result for HBs Ag will be exclusionary.

A negative result for HBs Ag will be tested (automatic reflex testing) for core antibodies (HBc Ab) and surface antibodies (HBs Ab).

- A negative test result for HBc Ab and HBs Ab does **not** require HBV DNA PCR qualitative testing and the subject may be enrolled ([Figure 2](#), Scenarios A and B).
- For a subject who has had a HBV vaccination (should document in the medical history), a positive test result for HBs Ab is expected and the subject may be enrolled ([Figure 2](#), Scenario B).\*
- A positive test result for HBc Ab requires HBV DNA PCR testing (automatic reflex testing) ([Figure 2](#), Scenarios C and D).
  - A positive result for HBV DNA or a result that exceeds detection sensitivity will be exclusionary.
  - A subject with a negative result for HBV DNA may be enrolled.

- For subjects in mainland China only: A positive result for HBs Ab/anti-HBs requires HBV DNA PCR testing.
  - A positive result for HBV DNA or a result that exceeds detection sensitivity will be exclusionary.
  - A subject with a negative result for HBV DNA may be enrolled.
  - For subjects with HBC Ab+ (irrespective of HBs Ab status) and negative HBV DNA at screening and a positive result for HBV DNA PCR testing during the study who also manifest an ALT > 5 × ULN OR ALT/AST > 3 × ULN and either a total bilirubin > 2 × ULN or INR > 1.5 OR ALT/AST > 3 × ULN along with clinical signs of possible hepatitis, study drug will need to be interrupted immediately and a hepatologist consultation should occur within 1 week for recommendation regarding subsequent treatment.

**Figure 2. Criteria for HBV DNA PCR Qualitative Testing**

\* For subjects who have had a HBV vaccination (should document in the medical history), a positive test result for HBs Ab is expected and these subjects may be enrolled. For subjects without a history of HBV vaccination, a positive result for HBs Ab/anti-HBs requires HBV DNA PCR testing.

\*\* For mainland China only: subjects with HBs Ab+ and/or HBc Ab+ and negative HBV DNA at screening, HBV DNA PCR test should be performed every 12 weeks. HBV DNA PCR testing every 12 weeks is not necessary when the subject has a history of HBV vaccine and HBs Ab+.

*Hepatitis C:*

Blood samples for hepatitis C serology will be obtained at the Screening Visit. A subject will not be eligible for study participation if test results indicate active hepatitis C (HCV RNA detectable in any subject with anti HCV Ab).

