### **Period 1 (12-Week Randomized, Double-Blind Treatment Period)**

Period 1 will begin at the Baseline Visit (Day 1) and will end at the Week 12 Visit. At the Baseline Visit, subjects who meet all the inclusion criteria and none of the exclusion criteria described in Section 5.2.1 and Section 5.2.2 will be enrolled into the study and randomized to double-blind treatment. During this period of the study, subjects will visit the study site at Weeks 1, 2, 4, 8, and 12. A  $\pm$  3 day window is permitted around scheduled study visits. The study drug dose taken the day prior to the Week 12 visit is considered the last dose in Period 1. Subjects who complete Period 1, but decide not to continue in Period 2 should complete a 30 day follow-up visit after the last dose of study drug.

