### **Period 2 (Open Label 52-Week Extension Period)**

Period 2 will begin at the Week 12 visit after all assessments have been completed. During Period 2, subjects will have a study visit at Weeks 16, 20, 24, 36, 48 and 64/PD. A  $\pm$  7 day window is permitted around scheduled study visits. At Week 24, if a subject fails to meet LDA criterion (LDA defined as CDAI  $\leq$  10) investigator should adjust the subject's background RA therapies. Starting at Week 24, at least 20% improvement in BOTH TJC AND SJC compared to baseline is required to remain in the study. Anyone

who does not fulfill this criterion at 2 consecutive visits (starting at Week 24) (see Section 5.2.3.1) must be discontinued from the study.

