- test for hepatitis B core antibody (HBc Ab) positive (+) subjects; (and for Hepatitis B surface antibody positive [+] subjects in mainland China only); or HCV ribonucleic acid (RNA) detectable in any subject with anti-HCV antibody (HCV Ab), syphilis antibody (subjects in mainland China only) or HIV antibody (HIV Ab).
- 12. History of symptomatic herpes zoster infection (within 12 weeks prior to the first dose of study drug), recurrent or disseminated (even a single episode) herpes zoster, or disseminated (even a single episode) herpes simplex.
  - 13. Subject has active TB or meets TB exclusionary parameters (refer to Section [5.3.1.1](#) for specific requirements for TB testing).
  - 14. Systemic use of known strong cytochrome P450 (CYP)3A inhibitors or strong CYP3A inducers from Screening through the end of the study (refer to [Table 2](#) for examples of commonly used strong CYP3A inhibitors and inducers).
  - 15. Receipt of any live vaccine < 4 weeks prior to the first dose of study drug, or expected need of live vaccination during study participation including at least 4 weeks after the last dose of study drug.
  - 16. History of any malignancy except for successfully treated NMSC or localized carcinoma in situ of the cervix.
  - 17. History of clinically significant (per Investigator's judgment) drug or alcohol abuse within the last 6 months.
  - 18. History of gastrointestinal perforation (other than appendicitis or penetrating injury) diverticulitis or significantly increased risk for GI perforation per investigator judgment.
  - 19. Conditions that could interfere with drug absorption including but not limited to short bowel syndrome.
  - 20. Subject has been a previous recipient of an organ transplant.

21. History of clinically significant medical conditions (including but not limited to clinically significant cardiac, hepatic, neurologic, respiratory, hematologic, gastrointestinal, renal, or psychiatric disease), or any other reason that in the opinion of the Investigator would interfere with the subject's participation in this study or would make the subject an unsuitable candidate to receive study drug.
22. Active infection(s) requiring treatment with parenteral anti-infectives within 30 days, or oral anti-infectives within 14 days prior to the first dose of study drug.
23. History of an allergic reaction or significant sensitivity to constituents of the study drug (and its excipients) and/or other products in the same class.

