**Table 5. Studies Activities (Period 2) (Continued)**

- n. For mainland China only, subjects with HBs Ab+ and/or HBc Ab+ and negative HBV DNA at screening, HBV DNA PCR test should be performed every 12 weeks. HBV DNA PCR testing every 12 weeks is not necessary when the subject has a history of HBV vaccine and HBs Ab+.
  - o. CDAI calculation requires input of SJC28 + TJC28 + PtGA + PhGA into IRT system. At Week 24, investigator should optimize background RA therapies in subjects who failed to achieve CDAI  $\leq$  10.
  - p. In Vivo Pharmacodynamic biomarker samples will not be collected for subjects in mainland China.
- Note:** Visit window is  $\pm$  7 days for the study. Any of the procedures may be performed at an unscheduled visit at the discretion of the Investigator.

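### The HBV DNA screening trigger for surface-antibody-positive, core-antibody-negative subjects is inconsistent across the protocol, and the 12-weekly follow-up test has no scheduled visit at Week 60

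*Protocol*

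**What the plan says.** **Screening.** Four statements in the protocol bear on a subject who is HBs Ag negative and HBs Ab positive.

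- Section 5.2.2, Exclusion Criterion 11, makes detected HBV DNA exclusionary for HBc Ab-positive subjects, then adds "and for Hepatitis B surface antibody positive [+] subjects in mainland China only". It has no exception for vaccination.
- Section 5.3.1.1, Hepatitis B, has a bullet that reads "For subjects in mainland China only: A positive result for HBs Ab/anti-HBs requires HBV DNA PCR testing". It too has no exception for vaccination.
- An earlier bullet in the same list says that after HBV vaccination "a positive test result for HBs Ab is expected and the subject may be enrolled". It has no country limit and does not mention PCR.
- The single-asterisk footnote to Figure 2 repeats the vaccination bullet and continues: "For subjects without a history of HBV vaccination, a positive result for HBs Ab/anti-HBs requires HBV DNA PCR testing". It has no country limit.

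A positive HBc Ab triggers PCR everywhere, and no passage disagrees with that.

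**Follow-up.** For mainland China subjects who are HBs Ab and/or HBc Ab positive with negative HBV DNA at screening, Table 5 footnote n says "HBV DNA PCR test should be performed every 12 weeks". Table 3 footnote s, Table 6 footnote e and the double-asterisk footnote to Figure 2 give the same rule. All four carry the same exemption: "HBV DNA PCR testing every 12 weeks is not necessary when the subject has a history of HBV vaccine and HBs Ab" is positive. On visits, Section 5.1 says for Period 1 that "subjects will visit the study site at Weeks 1, 2, 4, 8, and 12", and for Period 2 that "subjects will have a study visit at Weeks 16, 20, 24, 36, 48 and 64/PD", with a window of 7 days either side in Period 2.

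**The concern.** Criterion 11 and the China bullet make region the trigger for PCR after a positive HBs Ab. The Figure 2 footnote makes vaccination history the trigger. The two rules give different answers for some subjects, so two sites could screen the same patient differently, each with protocol text to rely on.

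The test is a safety screen whose result can exclude a subject, and Section 6.1.7 asks for infection work-up suited to an immunocompromised subject. There is also a classification problem. SAP Section 6.4 counts entry despite unmet criteria as an ICH deviation, and SAP Section 5.1 treats ICH deviations as major, which removes a subject from the Per Protocol Analysis Set. If the entry rule can be read two ways, so can the deviation.

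On follow-up, a stated 12-week interval needs a visit about every 12 weeks, and the schedule stops providing one after Week 48.

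**Working it through.** **1. Screening rules side by side.** The inputs are the four screening statements. For an HBs Ab-positive subject there are 2 regions × 2 vaccination histories × 2 HBc Ab results = 8 combinations. In the four HBc Ab-positive combinations PCR is required on every reading. The other four, all HBc Ab negative, are:

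| Region | Vaccinated | Criterion 11 and China bullet | Vaccination bullet and Figure 2 footnote | Result |
|---|---|---|---|---|
| Mainland China | No | PCR | PCR (footnote) | Agree |
| Mainland China | Yes | PCR | May enrol; PCR not mentioned | Ambiguous |
| Elsewhere | No | No PCR trigger | PCR (footnote) | Conflict |
| Elsewhere | Yes | No PCR trigger | May enrol; PCR not mentioned | Agree |

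So 4 + 2 = 6 combinations agree and 2 do not.

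**2. The conflict outside mainland China.** A site that omits PCR for an unvaccinated subject follows Criterion 11 and the body text but breaches the footnote. A site that does the PCR follows the footnote, but if DNA is detected, Criterion 11 does not exclude the subject: its HBV DNA clause covers HBc Ab-positive subjects anywhere and HBs Ab-positive subjects in mainland China only. The body text is no different, since its two statements that a positive result excludes sit under the HBc Ab bullet and the China bullet. Only the Investigator's discretion under Exclusion Criterion 10 (unsuitable because of a viral infection) is left.

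**3. Follow-up dates.** Multiples of 12 weeks up to Week 64 are 12, 24, 36, 48 and 60. The scheduled visits are Weeks 1, 2, 4, 8, 12, 16, 20, 24, 36, 48 and 64. The first four due dates each fall on a visit; Week 60 does not.

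- Nominal gap after Week 48: 64 − 48 = 16 weeks.
- Shortest gap with 1-week windows: (64 − 1) − (48 + 1) = 14 weeks.
- Longest gap: (64 + 1) − (48 − 1) = 18 weeks.
- For comparison, Week 36 to Week 48 is nominally 12 weeks, and at most (48 + 1) − (36 − 1) = 14.

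The shortest in-window gap after Week 48 thus equals the longest from Week 36 to Week 48, and no use of the windows brings it down to 12.

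**The case against.** Several points on the other side are sound.

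- **Unscheduled testing is allowed.** The note under Table 5 permits any procedure at an unscheduled visit, and Section 5.3.1.1 permits unscheduled laboratory tests at any time. A reader might infer that the 12-week interval cannot be met after Week 48. The documents do not support that: one due date lacks a scheduled visit. Those allowances are at the Investigator's discretion, however, and do not schedule the test.
- **Follow-up is worded consistently.** A reader might infer that like patients are monitored differently. They are not: the rule and its exemption are the same in all four places, the Week 60 gap affects every covered mainland China subject alike, and the limit to mainland China is an openly stated local rule.
- **The vaccinated mainland China case can be reconciled.** The vaccination bullet permits enrolment but does not waive PCR, whereas the protocol does waive it expressly for subjects negative on both antibodies. The China bullet can be read as a local addition. The follow-up exemption also sits within a group defined by negative HBV DNA at screening, which fits a screening PCR having been done. Against that, the footnote contrasts vaccinated with unvaccinated subjects when it requires PCR. This is therefore an ambiguity, not a flat contradiction.
- **Central testing may even out practice.** Hepatitis B serology and reflex PCR are central-laboratory tests. But only the HBc Ab bullet describes PCR as an automatic reflex, and vaccination history is recorded by the site. The text does not show which rule the laboratory would apply.
- **The Figure 2 graphic was not available for this check** and might narrow the footnote. The footnote's own words carry no country limit, though, and its asterisk is also attached to the general vaccination bullet in Section 5.3.1.1. The next footnote opens with an explicit mainland China limit.

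None of this removes the conflict for unvaccinated subjects outside mainland China.

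**Conclusion.** The point holds in a limited form. For HBs Ab-positive, HBc Ab-negative subjects, the protocol gives conflicting instructions on PCR outside mainland China when the subject is unvaccinated, and ambiguous ones in mainland China when the subject is vaccinated. The follow-up interval has no scheduled visit at Week 60; the 16-week gap (14 to 18 with windows) leaves it to unscheduled testing.

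The number of subjects affected cannot be stated. A reader might take the planned mainland China share, 222/322 = 69%, as the size of the problem. That is the expected enrolment there, not the number who are vaccinated, HBs Ab positive and HBc Ab negative, and the clearer conflict lies among the roughly 100 subjects from elsewhere. The documents give no antibody or vaccination rates for either group.

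No effect on the primary analysis or the sample size is shown. The primary analysis uses the Full Analysis Set; the possible statistical consequence is inconsistent deviation coding for the supportive Per Protocol analysis. The conclusion rests on the printed text and on reading the 12-week interval literally, counted from baseline or from the Week 48 test, which both give Week 60.

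**What to change.** 1. Reconcile Exclusion Criterion 11, the Hepatitis B bullets in Section 5.3.1.1 and the single-asterisk footnote to Figure 2 into one statement set out by region and vaccination history. For each group it should say whether a positive HBs Ab requires PCR and whether a detected result excludes the subject. The other places should refer to it.
2. Reconcile the 12-week interval in Table 3 footnote s, Table 5 footnote n, Table 6 footnote e and the double-asterisk footnote to Figure 2 with the Week 48 to Week 64 schedule in Section 5.1 and Table 5.
3. Before database lock, record how subjects already screened under either reading are to be classified as deviations.

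Which clinical rule applies is for the sponsor's medical team to settle. The cost is a clarification letter or amendment wording, plus a check that the central laboratory's reflex instructions match. The endpoints, sample size and primary analysis do not change.
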